Hypothesis 1C: CTI participants will have shorter time-to-follow-up with their primary providers.
3. Determine the effectiveness and cost-effectiveness of the ED-to-home CTI program for older adults treated in the ED and discharged home, as compared to usual care.
Hypothesis 2A: CTI participants will have increased patient activation 30 days after discharge.
Hypothesis 2B: CTI participants will have lower odds of repeat ED use within 30 days of discharge.
Hypothesis 2C: CTI participants will have lower estimated healthcare costs within 30 days of discharge.
4. Identify biomedical and psychosocial factors independently associated with repeat ED visits within 30 days of ED discharge among ED-to-home CTI program participants.
Hypothesis 3A: Biomedical factors associated with increased odds of repeat ED visits include increased age, increased number of comorbidities, impaired cognition, and limited functional status.
Hypothesis 3B: Psychosocial factors associated with increased odds of repeat ED visits include reduced social connectedness, increased anxiety symptoms, and increased depressive symptoms.

In this study, we will apply evidence-based findings to evaluate a program to help older adults remain healthy and independent after ED care. We will address a significant deficiency in the delivery of quality care for a uniquely vulnerable population: the ED-to-home transition of acutely ill older adults who do not require hospital admission. We will use an innovative approach by adapting the widely used CTI, which has been validated for hospital-to-home transitions, and deliver the services using paramedics, an underused, highly-skilled, and highly-respected resource present in all communities. This evidence will guide further efforts to optimize older adults' health following an ED visit, including dissemination and implementation of this ED-to-home CTI program and development of new approaches to target patients with repeat ED visits.

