12 DATA ANALYSIS AND MONITORING

12.1 SAMPLE SIZE DETERMINATION

This study is designed to have adequate power to test the primary hypotheses that the CTI will result in lower odds of repeat ED use within 30 days of discharge compared to the control group (Hypothesis 2B). Based on published data, we expect 20% of the subjects in the control group to have at least 1 repeat ED visit within the 30-day follow-up period. In order to detect a 5% absolute decrease in the frequency of repeat ED visits with 80% power using a Chi-square test at a two-sided significance level of 5%, we will need 860 subjects per group. We anticipate approximately 25% attrition over the 30-day follow up period. As such, a final sample size of 1200 subjects in each group will be recruited for participation. We also calculated the minimum detectable effect size testing individual biomedical and psychosocial factors predicting repeat ED visit in Aim 4 for intervention group only. With an expected 15% baseline proportion of repeat ED visit, the sample size of 860 in the intervention group will have 80% power to detect an odds ratio (OR) of 1.3 per standard deviation of a normally distributed predictor. Similarly, 80% power is available to detect an OR ranging from 1.6-1.7 for a binary predictor prevalent in 30-50% of subjects.

We will also have to adjust for clustering by site in most of the analyses below.

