12.2 PLANNED STATISTICAL ANALYSIS

Through the analytic methods used in Aims 2 and 3, we will assess differences between groups related to process outcome measures (Aim 2) and will assess the effectiveness and cost-effectiveness of the ED-to-home CTI (Aim 3). In Aim 4, we will identify predictors of repeat ED use among intervention group subjects. We will characterize of our study sample using descriptive statistics and corresponding measures of variation. We will assess for differences between groups at baseline despite randomization in key characteristics (e.g., demographics, comorbidities) using t-tests for continuous variables and Chi-square tests for categorical variables, using Fisher's exact test where appropriate. These comparisons will enable the identification of covariates to be controlled in our multivariable analyses. If distributional assumptions associated with a particular statistical procedure are violated, we will use appropriate transformations or non-parametric alternatives. Primary analyses will be performed under the intent-to-treat principle, keeping subjects in the group to which they were originally randomized, regardless of compliance or adherence to study procedures. We will conduct sensitivity analyses among subjects who complete all study procedures to evaluate the effect of the intervention among those who complete all study-related procedures. Hypothesis-driven comparisons will be made to control the family-wise type I error rate at 0.05 (two-sided) for the primary hypothesis.

Caregiver Subject Analysis: Although not an original aim of the study, we have obtained permission from the NIH and will perform a limited analysis of caregiver activation. This was only recently added to

the CTI. To compare the caregiver activation between the control and intervention groups, we will administer the FCAT. The FCAT will be scored as 1-6 points per question, for a score ranging from 10-60. We assume that 30% of participants will have caregivers with them, the average score will be 30, and we will look for a 5 point difference. Our sample size will allow a power of >0.8 for a t-test ($\alpha=0.05$).

Hyp 1A: More program participants will demonstrate understanding of their ED discharge instructions, red flags that indicate a worsening of their condition, and how to respond to the red flags three days after ED discharge.

Hyp 1B: More program participants will implement medication changes made in the ED within three days of ED discharge.

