include fixed and variable costs in our analysis while excluding costs associated with the research. We will evaluate the economic impact of CTI from the perspective of health care system/insurers, including both the cost of the CTI and the expected healthcare cost reduction due to altered use of ED, hospital, and office visits. Impact on direct healthcare costs (and hence analysis from the insurer perspective) will be most critical to the adoption and dissemination of this care model since insurance organizations (dominant stakeholders through control of payment), are unlikely to reimburse for CTI care unless they assess it as at cost-neutral or better.

The occurrence of events contributing to healthcare costs (e.g., ED visits) will be ascertained from clinical information systems at both health systems. We will estimate the following CTI expenses for the intervention group: hardware and/or software investments; maintenance costs; direct and indirect costs for training; personnel salary and benefit costs, etc. We will estimate the value of direct healthcare resources saved or expended, including both fixed and variable costs. We will use Medicare reimbursement schedules to assign costs to events because of their national scope, relevance to older populations, and alignment with the true costs of care rather than inflated costs or discounted insurance plan reimbursements. We will calculate total direct costs for each individual by taking the product of the costs per visit (price) and utilization by visit type, and summing across categories of utilization for that individual. We will then estimate unadjusted and adjusted incremental costs. The adjusted cost approach uses multivariable regression models to eliminate the effects of differences in population characteristics across comparison groups, if appropriate. To do so, we will estimate the program's monthly and annual costs using multivariable models and then will calculate the incremental cost of the CTI. All prices will be calculated in 2015 dollars. Using collected data, we will extrapolate the costs of running the program and expected benefits over 12-month period and annually. Finally, we will make economic projections of the program's financial sustainability and scalability. We will conduct a series of sensitivity analyses by modifying local wages, population case-mix and program effectiveness to estimate boundaries to program's sustainability and optimal operational conditions.

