To test the hypothesis that individual in the treatment group will have lower health care costs within the 30-days of ED discharge, we will first calculate total direct costs for each individual by taking the product of the costs per visit (price) and utilization by visit type, and summing across categories of utilization for that individual. We expect to find that total health care expenditures will exhibit a right skewed distribution with no negative measures and a nontrivial number of zeros. Consistent with the literature, we will log transform total spending to generate a normal distribution and use the box cox and GLM family test to find the distribution to best in our data. We will use the recycled predications method to re-transform estimates back from the log scale and compare average health care spending in the treatment and control groups.

Hyp. 3A: Biomedical factors associated with repeat ED visits include increased age, increased number of comorbidities, impaired cognition, and limited functional status.

Hyp. 3B: Psychosocial factors associated with repeat ED visits include reduced social connectedness, increased anxiety symptoms, and increased depressive symptoms.

To evaluate the relationship between biomedical and psychosocial factors with the occurrence of repeat ED visits among intervention subjects we will conduct bivariate analyses between patient characteristics and the primary outcome measure (repeat ED visits within 30 days). To do this we will conduct bivariate analyses with potential predictor variables and the dependent variable (repeat ED use) using two sample t-tests for continuous variables or Chi-Square tests for categorical variables, using Fisher's Exact test where appropriate. We will then identify independent predictors of repeat ED visits by fitting a multiple logistic regression model with biomedical and psychosocial factors identified in the bivariate analysis as independent variables. Model fitting statistics such as Akaike's Information Criteria and difference in log likelihood will inform the development of the final regression model. Standard diagnostic measures such

as residual plots will be used to assess the goodness-of-fit of the regression model assumptions and identify any outliers.

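### Hypothesis 2C: the plan expects zero costs but log transforms total spending, and does not commit the adjusted cost analysis to a method that accepts zeros

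*Combined protocol and SAP*

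**What the plan says.** All of this is in the combined protocol and SAP, section 12.2, under Hypothesis 2C unless stated otherwise.

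- Each patient's cost is built by "taking the product of the costs per visit (price) and utilization by visit type" and summing over visit types. A patient with no visits therefore costs exactly zero.
- The expected distribution is right skewed with "no negative measures and a nontrivial number of zeros".
- The next step is "we will log transform total spending to generate a normal distribution and use the box cox and GLM family test".
- Recycled predictions then serve to "re-transform estimates back from the log scale and compare average health care spending in the treatment and control groups". The target is thus mean spending by arm.
- The preceding paragraphs promise incremental cost both with and without adjustment, the adjusted version from multivariable regression with no family or link named. They describe an economic evaluation "including both the cost of the CTI and the expected healthcare cost reduction", whereas the hypothesis test is defined on visit cost alone.
- The opening of section 12.2 adds that if distributional assumptions fail, "we will use appropriate transformations or non-parametric alternatives". The Missing Data paragraph concerns unobserved values, and zeros are observed.

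No added constant, two-part model or other rule for zeros appears.

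**The concern.** Two adjacent sentences do not fit together. The plan predicts zeros and then prescribes a transformation that has no value at zero. An analyst who follows the text must either leave out the zero-cost patients or add a constant that the plan does not name.

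Leaving them out replaces the stated target, average spending per randomised patient, with average spending among patients who used care. That group is formed after randomisation. The trial's own hypotheses could shift its size in either direction: "CTI participants will have shorter time-to-follow-up with their primary providers" (Hypothesis 1C) could mean fewer zeros with CTI, and fewer repeat ED visits (2B) could mean more. Adding a constant instead makes the answer depend on an arbitrary number, unless the return to the cost scale is done in a way that undoes it. The plan does not say how that return is made.

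The cost result is meant to inform insurers, so the size of the mean difference matters as well as its sign.

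**Working it through.** The documents state no zero share, standard deviation or power for 2C, so there is no figure of the plan to reproduce. The check has four steps.

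**1. Do the named tools run on data with zeros?** The log of zero is minus infinity, so mean log cost is undefined once one zero is present. A standard routine for estimating the Box-Cox parameter (scipy) stops with a message that data must be positive. A fixed positive Box-Cox parameter does accept zero, but the plan does not fix one.

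**2. How many zeros?** This is not stated. Section 12.1 gives 20% repeat ED use in controls, and section 2.2 cites PCP follow-up in as few as 32% within 30 days. Counting only these two visit types, the zero share lies between 1 − (0.20 + 0.32) = 48% and 1 − 0.32 = 68%. Specialist and urgent care visits, or better PCP follow-up, would lower it. The illustrations below assume 5% to 25%.

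**3. Dropping zeros.** Let z be the zero share and m the mean cost among users, with subscripts C (control) and T (CTI). The overall mean is (1 − z)m, so:

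- users' ratio = true ratio × (1 − z_C)/(1 − z_T);
- with equal z, users' difference = true difference × 1/(1 − z).

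Equal shares: the ratio is unchanged. The difference is multiplied by 1/0.95 = 1.05 at 5% zeros, 1/0.90 = 1.11 at 10% and 1/0.80 = 1.25 at 20%. For a dollar figure, assume users' cost is lognormal (mu 7, sigma 1.2), with mean exp(7 + 1.2²/2) ≈ USD 2,253. At 20% zeros and a true ratio of 0.833, the true difference is 0.8 × 2,253 × 0.167 ≈ USD 300, and among users it is 2,253 × 0.167 ≈ USD 375.

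Unequal shares, true ratio 0.85:

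| Zeros, control vs CTI | Users' ratio |
|---|---|
| 20% vs 18% | 0.85 × 0.80/0.82 = 0.83 |
| 20% vs 22% | 0.85 × 0.80/0.78 = 0.87 |
| 20% vs 15% | 0.85 × 0.80/0.85 = 0.80 |
| 20% vs 25% | 0.85 × 0.80/0.75 = 0.91 |

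Simulation (2,000 trials per scenario, 900 per arm = 1,200 less 25% attrition, same lognormal) agrees: 0.830, 0.869, 0.801 and 0.906.

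**4. Adding a constant.** In the same simulation, log(cost + constant) was averaged by arm, returned to the cost scale with one smearing factor common to both arms (the mean exponentiated residual), and the constant subtracted.

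| Zeros, control vs CTI | True ratio | +0.01 | +1 | +100 |
|---|---|---|---|---|
| 5% vs 5% | 0.833 | 0.842 | 0.842 | 0.854 |
| 20% vs 20% | 0.833 | 0.863 | 0.864 | 0.875 |
| 20% vs 18% | 0.85 | 1.077 | 0.984 | 0.916 |
| 20% vs 22% | 0.85 | 0.712 | 0.781 | 0.858 |
| 20% vs 15% | 0.85 | 1.480 | 1.176 | 0.964 |
| 20% vs 25% | 0.85 | 0.526 | 0.659 | 0.818 |

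With an arm-specific smearing factor every constant returns the ratio of arm means (0.853 and 0.852 in the last two rows). Algebraically, exp(mean log) times the arm's own mean exponentiated residual is the arm mean of cost plus the constant.

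**Check of the remedy.** A log-link GLM with zeros kept, one baseline covariate, recycled predictions and robust standard errors gave 0.831 (true 0.833, equal 20%), 0.851 to 0.852 (true 0.85, 20% vs 15%) and 0.851 (true 0.85, 20% vs 25%). Interval coverage was 94% to 95% under gamma or Poisson variance.

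**The case against.** The best defence is that the paragraph can be read as a GLM plan. A GLM family test has little purpose if the model is least squares on log cost, and recycled predictions sit naturally with a log-link GLM, which accepts zeros. The unadjusted incremental cost is most simply a difference in arm means. That keeps zeros and would expose a poor adjusted model. The intention-to-treat statement in section 12.2 and the stated target of average spending also weigh against dropping patients.

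This stands in part. A workable analysis is open, and probably an unadjusted one is planned. But transforming spending itself and returning from the log scale describe a model for log cost, and nothing commits the adjusted analysis to a zero-retaining method. The generic fallback sets no rule for zeros, and a rank test would not compare means.

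It is also fair that the largest distortions come from strong assumptions. Ratios of 1.48 and 0.53 need a one-cent constant, a common smearing factor and a five-point gap in zero shares. None of these is in the documents, and the constant scenarios use smearing without covariates rather than the planned recycled predictions.

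**Conclusion.** The concern holds as a gap in specification. One stated step cannot be run on the data the plan expects, and the choice that replaces it is left to the analyst. If zeros are dropped, the mean cost difference is overstated by 1/(1 − zero share) with equal shares, 25% at an assumed 20%. With unequal shares the ratio also moves, to 0.80 or 0.91 for a true 0.85 in the five-point scenarios. A constant with a common retransformation has a modest effect on the ratio with equal shares and a strong one with unequal shares. Arm-specific smearing avoids this. The ratio results for dropped zeros follow from algebra given the shares. The constant results also depend on the assumed lognormal costs.

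Three other readings are tempting and are not supported. A reader might infer that the plan cannot estimate average cost, or that its result will have the wrong sign; the GLM and arm-mean readings are open, and no constant or retransformation is specified. A reader might infer that equal zero shares make the matter harmless; that is true of the ratio when zeros are dropped, but not of the mean difference. A reader might carry the concern over to the main result; section 12.1 ties sample size to "adequate power to test the primary hypotheses that the CTI will result in lower odds of repeat ED use", which this does not touch.

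**What to change.** In the last Hypothesis 2C paragraph of section 12.2, replace the log transformation of spending with a model that includes every randomised patient with cost data, zeros retained. A log-link GLM on untransformed visit cost, fitted by quasi-likelihood so that zeros are accepted whichever family is chosen, would do. The planned GLM family test can still choose the family. If Box-Cox is kept, describe it as a check of scale on the positive costs only. Apply the planned recycled predictions over all patients, and report the mean cost difference with a robust or bootstrap confidence interval next to the unadjusted difference in arm means. A two-part model that recombines to the overall mean is an acceptable alternative or sensitivity analysis.

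The cost is a few sentences and slightly more programming, with no new data. The drawback is wider intervals: at equal 20% zeros and a true ratio of 0.833, simulated power was 48% to 52% for the GLM against 82% for log cost among users. The latter answers a different question once zero shares differ.

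### Aim 4 names seven factors but estimates adjusted effects only for those that pass an unadjusted screen with no stated threshold; one model with all seven should be the test of Hypotheses 3A and 3B

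*Combined protocol and SAP*

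**What the plan says.** Section 2.1 sets Aim 4 as finding the factors independently associated with a repeat ED visit within 30 days among subjects who received the program. Hypothesis 3A, repeated in section 12.2, names four biomedical factors: "increased age, increased number of comorbidities, impaired cognition, and limited functional status". Hypothesis 3B names three psychosocial ones: "reduced social connectedness, increased anxiety symptoms, and increased depressive symptoms". Table 2 lists a baseline measure taken in the ED for each of the seven.

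The analysis in section 12.2 has three steps:

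1. Candidates are tested one at a time: "we will conduct bivariate analyses with potential predictor variables and the dependent variable (repeat ED use) using two sample t-tests for continuous variables", with chi-square or Fisher's exact tests for categorical ones. No p-value threshold is given, and the candidate pool is not restricted to the seven.
2. A multiple logistic model is fitted with the "biomedical and psychosocial factors identified in the bivariate analysis as independent variables".
3. The choice of final model is described only in these terms: "Model fitting statistics such as Akaike's Information Criteria and difference in log likelihood will inform the development of the final regression model".

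Section 12.1 gives this aim its own power statement: "With an expected 15% baseline proportion of repeat ED visit, the sample size of 860 in the intervention group will have 80% power". The effect size it names for a continuous factor is "an odds ratio (OR) of 1.3 per standard deviation of a normally distributed predictor". That statement concerns individual predictors and makes no allowance for selection. For Aim 4 the plan has no forced-in factor, shrinkage, validation or correction for selection. The family-wise error statement in section 12.2 covers the primary hypothesis only.

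**The concern.** Independent association is a question about adjusted effects, and the hypotheses fix in advance which seven effects are in question. An unadjusted test is the wrong gate for it. A factor can be weak alone and matter after adjustment, and a factor that stops at the gate leaves its hypothesis untested as worded. Because no threshold is stated, two analysts could both follow section 12.2 and report different sets of factors.

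Selection also affects the numbers that are reported. A weak factor passes the screen mainly in samples where it is overestimated, and its ordinary standard error does not reflect this. Sections 1 and 2.2 say the results should help future programs meet recipients' needs. Section 2.0 of Appendix A cites the final aim as a reason for needing the full sample.

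**Working it through.** **Inputs from section 12.1.** n = 860 in the intervention group, 15% with a repeat visit, 80% power. The two-sided 5% level is stated there for the primary test and assumed here for Aim 4.

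**The plan's own figure.** For a standardized predictor, the standard error of ln(OR) is about 1/√(n·p·(1−p)) = 1/√(860 × 0.15 × 0.85) = 1/√109.65 = 0.0955. The detectable OR is exp[(1.960 + 0.842) × 0.0955] = 1.307, and power at OR 1.30 is 78.4%. For a binary predictor with 15% in the reference group, the detectable OR is 1.70, 1.65 and 1.64 at prevalence 30, 40 and 50%. The stated 1.3 and 1.6-1.7 are reproduced.

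**Is screening needed for lack of events?** No. 860 × 0.15 = 129 expected events, which is 129/7 = 18.4 per factor. With site and caregiver stratum added it is 129/9 = 14.3 per parameter.

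**What a screen does, one factor at a time.** At p<0.05 a factor passes only if its observed OR is at least exp(1.96 × 0.0955) = 1.21 per SD (or its reciprocal). With β = ln(OR), s = 0.0955, c = 1.96 and μ = β/s, the mean estimate given passing is

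β + s·[φ(c−μ) − φ(c+μ)] / [Φ(μ−c) + Φ(−μ−c)].

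For a true OR of 1.15, μ = 1.46. The chance of passing is 31% and the mean OR given passing is 1.28. For a true OR of 1.30, the figures are 78% and 1.35.

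**Simulation of the whole procedure.** The threshold, the elimination rule, the correlations and the true ORs are assumptions, because the documents give none. Settings: n = 860, 15% events, seven standard normal factors with true ORs of 1.3 (three), 1.15 (two) and 1.0 (two); pairwise correlation 0 or 0.3; t-test screen at p<0.05 or p<0.20, then backward AIC; 1,500 runs per setting. The comparison is one model with all seven factors.

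| | Planned selection | Seven-factor model, all reported |
|---|---|---|
| True OR 1.15: retained | about 28-52% of runs | always estimated |
| True OR 1.15: mean OR | about 1.25-1.29 if retained | about 1.15 |
| True OR 1.3: mean OR | 1.33-1.36 if retained | 1.30-1.31 |
| True OR 1.3: interval coverage | about 94-98% if retained | 94-96% |
| Null factor: interval coverage | about 14-74% if retained | 94-96% |
| Null factor: significant | 4-6% | 4-6% |
| True OR 1.3, correlation 0.3: significant | 70-71% | 64-66% |

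In a second mix that included factors with a true OR of 1.20, such a factor was dropped in about 32-53% of runs.

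**Same filter on both sides.** If the seven-factor model is read only where p<0.05, a true OR of 1.15 reads 1.29 at correlation 0 and 1.33-1.34 at correlation 0.3. That is as much inflation as under the planned procedure, or more.

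**The case against.** The strongest reply is that the left column of the table is conditional on retention and the right column is not. Put through the same significance filter, the full model inflates as much or more. This stands: most of the inflation comes from reporting only what passes, and a full model helps only if all seven estimates are shown.

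A reader might infer that the plan yields inflated odds ratios and invalid confidence intervals for every factor it reports. That is too strong. At the OR of 1.3 for which the aim is powered, coverage is near nominal and the inflation small. Failure is concentrated in null or very weak factors that survive. Section 12.2 does not say that intervals will be reported for Aim 4, does not name backward elimination (AIC only informs the model) and does not fix a p-value.

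A reader might also infer more false positives because null factors correlated with real ones pass an unadjusted screen. They are retained somewhat more often, but null factors that are both retained and significant are no more frequent than in the full model. With correlated predictors, the planned procedure also detects real effects slightly more often.

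Finally, Aim 4 is a secondary, non-randomized analysis in one arm. That limits the priority of the point. It does not explain why seven factors named in advance should have to earn their adjusted estimates through an unadjusted test.

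**Conclusion.** The point holds as a mismatch between hypothesis and analysis. Seven factors are prespecified, the question is adjusted association, and the stated procedure gives no adjusted estimate for a named factor that fails an unspecified unadjusted screen. The conclusion rests on the text of sections 2.1 and 12.2 and on the 129 expected events, which remove any sample-size reason for screening.

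The numerical harm is modest and depends on the simulation assumptions, including normally distributed factors. It matters for weak effects (a true 1.15 reading as roughly 1.25-1.29) and for null factors that are retained. It is small near OR 1.3, and the false-positive rate does not rise. The change should be made, but Hypothesis 2B and the rest of the randomized comparison do not depend on it.

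**What to change.** In section 12.2, name one logistic model as the test of Hypotheses 3A and 3B. It contains all seven named factors (continuous where measured so) plus site and the caregiver stratum used in randomization. Report all seven adjusted odds ratios with 95% confidence intervals, whatever their significance. Keep the bivariate results as description. Label any AIC-selected model that brings in other characteristics as exploratory, and state its screening threshold.

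The cost is a change of wording: no new data, no extra subjects, and less analysis work than the stated procedure. The price is slightly lower power for individual factors when predictors are correlated (about 64-66% against 70-71% at OR 1.3 and correlation 0.3).
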